8.3.5.2. Exposure During Breastfeeding

An exposure during breastfeeding occurs if:

A female participant is found to be breastfeeding while receiving or after discontinuing study intervention.

- A female participant is found to be breastfeeding while receiving or after discontinuing study intervention.
- A female is found to be breastfeeding while being exposed or having been exposed to study intervention (ie, environmental exposure). An example of environmental exposure during breastfeeding is a female family member or healthcare provider who reports that she is breastfeeding after having been exposed to the study intervention by inhalation or skin contact.

The investigator must report exposure during breastfeeding to Pfizer Safety within 24 hours of the investigator's awareness, irrespective of whether an SAE has occurred. The information must be reported using the CT SAE Report Form. When exposure during breastfeeding occurs in the setting of environmental exposure, the exposure information does not pertain to the participant enrolled in the study, so the information is not recorded on a CRF. However, a copy of the completed CT SAE Report Form is maintained in the investigator site file.

An exposure during breastfeeding report is not created when a Pfizer drug specifically approved for use in breastfeeding women (eg, vitamins) is administered in accord with authorized use. However, if the infant experiences an SAE associated with such a drug, the SAE is reported together with the exposure during breastfeeding.

8.3.5.3. Occupational Exposure

An occupational exposure occurs when a person receives unplanned direct contact with the study intervention, which may or may not lead to the occurrence of an AE. Such persons may include healthcare providers, family members, and other roles that are involved in the trial participant's care.

The investigator must report occupational exposure to Pfizer Safety within 24 hours of the investigator's awareness regardless of whether there is an associated SAE. The information must be reported using the CT SAE Report Form. Since the information does not pertain to a participant enrolled in the study, the information is not recorded on a CRF; however, a copy of the completed CT SAE Report Form is maintained in the investigator site file.

8.3.6. Cardiovascular and Death Events

Not applicable.

8.3.7. Disease -Related Events and/or Disease -Related Outcomes Not Qualifying as AEs or SAEs

Not applicable.

8.3.8. Adverse Events of Special Interest

Not applicable.

8.3.8.1. Lack of Efficacy

This section is not applicable because efficacy is not expected in the study population.

8.3.9. Medical Device Deficiencies

Not applicable.

8.3.10. Medication Errors

Medication errors may result from the administration or consumption of the study intervention by the wrong participant, or at the wrong time, or at the wrong dosage strength.

Exposures to the study intervention under study may occur in clinical trial settings, such as medication errors.

| Safety Event | Recorded on the CRF | Reported on the CT SAE Report Form to Pfizer Safety Within 24 Hours of Awareness |
|---------------------|---|---|
| Medication errors | All (regardless of whether associated with an AE) | Only if associated with an SAE |

Medication errors include:

- Medication errors involving participant exposure to the study intervention;
- Potential medication errors or uses outside of what is foreseen in the protocol that do or do not involve the study participant.

Such medication errors occurring to a study participant are to be captured on the medication error page of the CRF, which is a specific version of the AE page.

In the event of a medication dosing error, the sponsor should be notified within 24 hours.

Whether or not the medication error is accompanied by an AE, as determined by the investigator, the medication error is recorded on the medication error page of the CRF and, if applicable, any associated AE(s), serious and nonserious, are recorded on the AE page of the CRF.

Medication errors should be reported to Pfizer Safety within 24 hours on a CT SAE Report Form **only when associated with an SAE**.

8.4. Treatment of Overdose

For this study, any dose of PF-06480605 greater than 500 mg within 2-weeks will be considered an overdose.

Sponsor does not recommend specific treatment for an overdose.

In the event of an overdose, the investigator should:

1. Contact the medical monitor within 24 hours.
2. Closely monitor the participant for any AEs/SAEs and laboratory abnormalities for at least 5 half-lives or 28 calendar days after the overdose of PF06480605 (whichever is longer).
3. Document the quantity of the excess dose as well as the duration of the overdose in the CRF.
4. Overdose is reportable to Safety **only when associated with an SAE**.

5. Obtain a blood sample for PK analysis within 1 day from the date of the last dose of study intervention if requested by the medical monitor (determined on a casebycase basis).

Decisions regarding dose interruptions or modifications will be made by the investigator in consultation with the medical monitor based on the clinical evaluation of the participant.

8.5. Pharmacokinetics

Blood samples of approximately 3 mL, to provide approximately 1.2 mL serum, will be collected for measurement of serum concentrations of PF-06480605 as specified in the [SoA](#). Instructions for the collection and handling of biological samples will be provided in the laboratory manual or by the sponsor. The actual date and time (24-hour clock time) of each sample will be recorded.

The actual times may change, but the number of samples will remain the same. All efforts will be made to obtain the samples at the exact nominal time relative to dosing. Collection of samples up to and including 10 hours after dose administration that are obtained within 10% of the nominal time relative to dosing (eg, within 6 minutes of a 60-minute sample) will not be captured as a protocol deviation, as long as the exact time of the collection is noted on the source document and data collection tool (eg, CRF/DCT). Collection of samples more than 10 hours after dose administration that are obtained ≤ 1 hour away from the nominal time relative to dosing will not be captured as a protocol deviation, as long as the exact time of the collection is noted on the source document and data collection tool (eg, CRF/DCT). In follow-up visits (after Day 5), collection of samples that are obtained within 3 days of planned visit will not be captured as a protocol deviations, as long as the exact time of the collection is noted on the source document and data collection tool (eg, CRF/DCT).

Samples will be used to evaluate the PK of serum PF-06480605 concentration. Samples collected for analyses of serum PF-06480605 concentration may also be used to evaluate safety or efficacy aspects related to concerns arising during or after the study, for metabolite identification and/or evaluation of the bioanalytical method. [CCI](#)

Genetic analyses will not be performed on these serum samples. Participant confidentiality will be maintained.

Samples collected for measurement of serum concentrations of PF-06480605 will be analyzed using a validated analytical method in compliance with applicable SOPs.

The PK samples must be processed and shipped as indicated in the instructions provided to the investigator site to maintain sample integrity. Any deviations from the PK sample handling procedure (eg, sample collection and processing steps, interim storage or shipping conditions), including any actions taken, must be documented and reported to the sponsor. On a case-by-case basis, the sponsor may make a determination as to whether sample integrity has been compromised.

Drug concentration information that would unblind the study will not be reported to investigator sites or blinded personnel until the study has been unblinded.

Any changes in the timing or addition of time points for any planned study assessments must be documented and approved by the relevant study team member and then archived in the sponsor and site study files, but will not constitute a protocol amendment. The IRB/EC will be informed of any safety issues that require alteration of the safety monitoring scheme or amendment of the ICD.

8.6. Pharmacodynamics

Blood samples of approximately 8 mL, to provide approximately 3 mL serum, will be collected into appropriately labeled collection tubes (no additives). Serum samples will be collected and aliquoted for the analysis of serum sTL1A at times specified in the [SoA](#).

The actual times may change, but the number of samples will remain the same. All efforts will be made to obtain the samples at the exact nominal time relative to dosing. Collection of samples up to and including 10 hours after dose administration that are obtained within 10% of the nominal time relative to dosing (eg, within 6 minutes of a 60-minute sample) will not be captured as a protocol deviation, as long as the exact time of the collection is noted on the source document and data collection tool (eg, CRF/DCT). Collection of samples more than 10 hours after dose administration that are obtained ± 1 hour away from the nominal time relative to dosing will not be captured as a protocol deviation, as long as the exact time of the collection is noted on the source document and data collection tool (eg, CRF/DCT). In follow-up visits (after Day 5), collection of samples that are obtained within 3 days of planned visit will not be captured as a protocol deviations, as long as the exact time of the collection is noted on the source document and data collection tool (eg, CRF/DCT).

As part of understanding the PD of the study intervention, samples may be used for evaluation of the bioanalytical method, [CCI](#)

Samples will be analyzed using a validated analytical method in compliance with applicable SOPs.

The PD samples must be processed and shipped as indicated in the instructions provided to the investigator site to maintain sample integrity. Any deviations from the PD sample handling procedure (eg, sample collection and processing steps, interim storage, or shipping conditions), including any actions taken, must be documented and reported to the sponsor. On a case-by-case basis, the sponsor may make a determination as to whether sample integrity has been compromised.

8.7. Genetics

8.7.1. Specified Genetics

Genetics (specified analyses) are not evaluated in this study.

8.8. Biomarkers

Biomarkers are not evaluated in this study.

8.9. Immunogenicity Assessments

Blood samples of approximately 3 mL, to provide approximately 1.2 mL serum, will be collected for determination of anti-drug antibodies (ADA) and neutralizing antibodies (NAb) as specified in the [SoA](#). Instructions for the collection and handling of biological samples will be provided in the laboratory manual or by the sponsor. The actual date and time (24-hour clock time) of each sample will be recorded.

Samples collected for determination of anti-drug antibodies (ADA) and neutralizing antibodies (NAb) may also be used for additional characterization of the immune response and/or evaluation of the bioanalytical method, [CCI](#)

Genetic analyses will not be performed on these serum samples. Participant confidentiality will be maintained.

Samples will be analyzed using a validated analytical method in compliance with applicable SOPs. Samples determined to be positive for ADA may be further characterized for NAb.

The immunogenicity samples must be processed and shipped as indicated in the instructions provided to the investigator site to maintain sample integrity. Any deviations from the immunogenicity sample handling procedure (eg, sample collection and processing steps, interim storage, or shipping conditions), including any actions taken, must be documented and reported to the sponsor. On a case-by-case basis, the sponsor may make a determination as to whether sample integrity has been compromised.

Immunogenicity information that would unblind the study will not be reported to investigator sites or blinded personnel until the study has been unblinded.

Any changes in the timing or addition of time points for any planned study assessments must be documented and approved by the relevant study team member and then archived in the sponsor and site study files, but will not constitute a protocol amendment. The IRB/EC will be informed of any safety issues that require alteration of the safety monitoring scheme or amendment of the ICD.

8.10. Health Economics

Health economics/medical resource utilization and health economics parameters are not evaluated in this study.

9. STATISTICAL CONSIDERATIONS

Detailed methodology for summary and statistical analyses of the data collected in this study is outlined here and further detailed in a SAP, which will be maintained by the sponsor. The SAP may modify what is outlined in the protocol where appropriate; however, any major

modifications of the primary endpoint definitions or their analyses will also be reflected in a protocol amendment.

9.1. Statistical Hypotheses

No formal statistical hypothesis testing will be conducted for PK/PD and safety analyses.

9.2. Sample Size Determination

The maximum sample size of approximately 24 participants is not based on any statistical considerations. Those participants will be enrolled and receive the study intervention such that approximately 12 participants are assigned to each cohort (450 mg and 150 mg) to ensure that 11 evaluable participants per cohort will complete the study. In each cohort, 12 participants will be randomly assigned at an allocation ratio of 3:1 to the active treatment and placebo arms.

Participants will be enrolled to both cohorts sequentially, starting with the 450 mg cohort first. When the 150 mg cohort is determined to be needed, the 150 mg cohort with entirely new participants will be opened. The 150 mg cohort will be started only if it indicates the ethnic PK difference (eg, more than two-fold higher exposure) based on all available serum concentrations data of PF-06480605 obtained until the timing the PK sample is collected at Day 14 after administration, by comparing the dose-normalized mean exposures (or dose-normalized mean concentrations profiles) in this study versus dose-normalized mean exposures in Western study B7541001 and Japanese study B7541006. If the 150 mg is not needed, then only approximately 12 participants will be administered the study intervention or placebo.

| Cohort | Treatment | Number of participants |
|---------------|--------------------|-------------------------------|
| 1 | PF-06480605 450 mg | 9 |
| | Placebo | 3 |
| 2 (optional) | PF-06480605 150 mg | 9 |
| | Placebo | 3 |

Participants, who drop out from the study if the number of participants completing at least the follow-up visit at Day 57 per cohort decreases to 10 or lower, will be replaced.

If a participant discontinues before completing the part of the study to which they have been randomized, or withdraws for reasons unrelated to the safety of the study intervention, the participant may be replaced at the discretion of the investigator upon consultation with the sponsor.

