Within 28 days of successful completion of the screening process, eligible participants will be enrolled and randomized to receive a single dose of PF-06480605 450 mg or 150 mg (if needed) or placebo. Participants will be admitted into the CRU approximately 1 day prior to dosing and required to stay overnight in the CRU at least through completion of the Day 5 evaluations. Participants will return for outpatient follow-up visits through Day 114.

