The study duration and frequency of each assessment were decided based on information of previous studies. Day 114 was considered the necessary period to reduce blood levels sufficiently, and no treatment-related AEs were observed after Day 85 in previous studies. Sample collection points for PK, immunogenicity and PD were selected based on the results in Study B7541001 and/or Study B7541006. In addition, based on considering the clinical practice and minimal necessity for PK evaluation, participants, who drop out from the study if the number of participants completing at least the follow-up visit at Day 57 per cohort decreases to 10 or lower, will be replaced.

It is common to use a double-blind design (participant- and investigator-blinded) with placebo control to evaluate the safety and tolerability of the drug, while sponsor is open to allow more efficient decision-making, especially in early stage of the development.

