4.4. End of Study Definition

A participant is considered to have completed the study if he/she has completed all phases of the study, including the last visit.

The end of the study is defined as the date of the last visit of the last participant in the study.

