9.3. Analysis Sets

For purposes of PK and safety analyses, the following analysis sets are defined:

| | |
|-----------------------------|--|
| Safety Analysis Set | All randomized participants who applied at least 1 dose of study intervention. |
| PK Concentration Set | All randomized participants who applied at least 1 dose of study intervention and for whom at least 1 concentration value is reported. |
| PK Parameter Set | All randomized participants who applied at least 1 dose of study intervention and for whom at least 1 of the PK parameters of interest (eg, AUC_{inf} and C_{max}) is calculated. |
| Immunogenicity Analysis Set | All randomized participants who applied at least 1 dose of study intervention with at least 1 post-treatment anti-drug (PF-06480605) antibody determination. |
| PD Analysis Set | All randomized participants who have at least 1 PD assessment. |

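### Does the promise of 11 study completers per cohort need rewording, when mandatory replacement secures 11 only to Day 57?

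*Protocol*

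**What the plan says.** The size statement in Protocol 9.2 is that about 12 participants are assigned to each cohort (9 active, 3 placebo) "to ensure that 11 evaluable participants per cohort will complete the study". The same phrase stands twice in the Synopsis (Protocol 1.1), in Protocol 4.1 and in SAP 2.2. Protocol 9.2 also says that the maximum of about 24 "is not based on any statistical considerations".

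Protocol 4.4 defines completion: "A participant is considered to have completed the study if he/she has completed all phases of the study, including the last visit". Protocol 4.1 and the schedule in 1.3 place the last visit at Day 114: "Participants will return for outpatient follow-up visits through Day 114".

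Two replacement rules accompany the size statement in each of these sections. The mandatory one applies to dropouts "if the number of participants completing at least the follow-up visit at Day 57 per cohort decreases to 10 or lower". The other covers anyone who stops before finishing their part of the study, or who withdraws for reasons unrelated to safety; in that case "the participant may be replaced at the discretion of the investigator upon consultation with the sponsor". Protocol 4.2 explains the mandatory rule as "based on considering the clinical practice and minimal necessity for PK evaluation".

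**The concern.** Read literally, the size statement and the replacement rule guarantee different things. A participant who leaves after Day 57 has already completed Day 57, so the departure cannot trigger mandatory replacement. If 11 reach Day 57 and one then leaves, the cohort has 10 completers in the sense of Section 4.4, and only a discretionary rule is available. The word 'evaluable' does not settle the matter, because neither Protocol 9.3 nor SAP 4 defines it.

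The samples exposed are those of Day 85 and Day 114. They inform the terminal phase, and so AUCinf and the half-life (both primary, as data permit), as well as late ADA, NAb and sTL1A results. A reader of the Synopsis might expect at least 11 full profiles per cohort (active and placebo together) and find fewer.

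**Working it through.** **Bookkeeping.** 12 at 3:1 is 9 + 3. Two cohorts give 24 = 18 + 6. Both agree with the tables. The documents give no dropout rate behind the step from 11 to 12, so there is no sample size formula to reproduce.

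**Is 12 a reasonable number for 11 completers?** The only dropout figures in the documents for a placebo-controlled study in healthy participants are in Protocol 2.2.2.1.1 (B7541001): 3 of 60 in the single-dose period, and 6 of 92 over both periods.

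- Inflation, 11/(1 − p): 11/0.950 = 11.6 and 11/0.935 = 11.8. Both round up to 12.
- Expected completers, 12(1 − p): 11.4 and 11.2.
- Chance that at least 11 of 12 complete with no replacement at all (binomial): 0.882 and 0.818.

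So 12 is a sensible planning figure, although it does not ensure 11.

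**How often would a cohort finish below 11?** Assume a constant hazard over the 113 days from dosing to Day 114, no discretionary replacement, and B7541001 dropout read as a 113-day risk (its follow-up length is not stated). Retention to Day 57 is S = (1 − p)^(56/113). Retention from Day 57 to Day 114 is q = (1 − p)^(57/113).

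| Quantity | p = 3/60 | p = 6/92 |
|---|---|---|
| S; q | 0.9749; 0.9745 | 0.9671; 0.9666 |
| P(12 at Day 57) = S^12 | 0.7371 | 0.6696 |
| P(11 at Day 57) = 12·S^11·(1 − S) | 0.2277 | 0.2731 |
| P(10 or fewer finish, from 12) | 0.0363 | 0.0591 |
| P(10 or fewer finish, from 11) = 1 − q^11 | 0.2477 | 0.3122 |
| Below 11, mandatory rule never triggered | 0.083 | 0.125 |
| P(10 or fewer at Day 57), then topped up to 11 | 0.0352 | 0.0573 |
| Below 11, topped-up cohorts included | 0.092 | 0.143 |

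For 3/60 the first total is 0.7371 × 0.0363 + 0.2277 × 0.2477 = 0.083. Adding 0.0352 × 0.2477 = 0.009 gives 0.092. If no dropout falls after Day 57, both totals are zero. Any discretionary replacement lowers them.

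**What uses the 11?**

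- Analysis sets: the PK Parameter Set takes treated participants "for whom at least 1 of the PK parameters of interest" is calculated. No set asks for Day 57 or Day 114 completion.
- Endpoints: losses after Day 57 cannot alter the 14-day AUC and are not expected to alter Cmax or Tmax. In SAP 5.3.3 a parameter that cannot be derived is set to missing.
- Decision on the 150 mg cohort: it rests on concentrations to Day 14.
- Inference: none is planned (Protocol 9.1, SAP 5.1).
- Reporting: SAP 6.1.1 gives n for each PK parameter and SAP 6.4.2 summarises discontinuations and disposition, so the achieved numbers will be visible.

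**The case for a change.** The best case for acting is that the figure of 11 is the only reason the protocol gives for 12 per cohort, and a stated reason should match the rule that delivers it. 'Ensure' is a strong word, and a rule under which a participant may be replaced cannot support it. The late visits have a purpose as well: Protocol 4.2 treats Day 114 as the time needed for blood levels to fall sufficiently. The subcutaneous half-lives in Protocol 2.2.2.3.1 run up to 21 days, with the longer values at 100 and 300 mg. At 21 days, Day 57 is only 56/21 = 2.7 half-lives after dosing, so a participant lost then may yield a weaker AUCinf and half-life.

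The textual point stands: the phrase claims more than the mandatory rule secures. The appeal to late data does not support a rewording, because restating the target at Day 57 would collect no Day 85 or Day 114 sample. Nor is there a case for extending the mandatory rule. Protocol 4.2 shows that Day 57 was chosen on purpose as the least needed for PK, and the discretionary rule already allows later losses to be made good where the sponsor and investigator think it worthwhile.

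**Conclusion.** No change is needed. The phrase is a planning aim attached to an approximate, non-statistical size, and the rule that governs conduct is printed in the same sections and justified in Protocol 4.2. Anyone running the trial would follow that rule, and anyone analysing it would use the defined analysis sets, which do not depend on the 11.

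The shortfall is small. Expected completers are 11.2 to 11.4 of 12. The chance of finishing below 11 is roughly 9% to 14% under even dropout with no discretionary replacement, and zero if dropout is early. Those figures are illustrative: the timing of dropout is assumed, and the rates come from 3 and 6 events in another study. The conclusion does not rest on them. It rests on the absence of any analysis, decision or claim that uses the number. Tidier wording would be harmless, but it would leave the design, the data and the conclusions as they are.
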